16.2.2.4 Outcome of Adverse Event

The Investigator must assess the outcome of each adverse event as: unresolved, resolved, resolved with sequelae, unknown, or death.

16.2.2.5 Indication of Seriousness of Adverse Event

For each adverse event, the Investigator must determine if the adverse event meets the criteria for a Serious Adverse Event (SAE) as defined in Section 16.2.6.

16.2.3 Dental Adverse Events

Dental and oral health will be followed closely throughout the course of the study, with exams performed by either a licensed dentist (DDS or DMD) at each site, or oral examination by the Investigator. Dental adverse events (i.e., anything related to oral and dental health) will be reported as such if:

- Any finding from the dental or oral exam is determined to be clinically significant or require treatment/follow-up with a dentist, in the opinion of the Investigator or study dentist.
- An issue related to tooth or mouth discomfort is mentioned by the subject in response to a traditional non-leading question (e.g., “how have you been feeling since the last time I saw you?”).

All adverse events meeting the classification of “dental adverse events” will be included in the all adverse events analysis, as well as designated as a dental adverse event in the adverse event eCRF to enable appropriate safety sub-analyses.

16.2.4 Adverse Events of Special Interest

Adverse events indicative of compromised airway protection as manifested by aspiration, aspiration pneumonia, choking, and dysphagia will be closely evaluated as adverse events of special interest (AESI). In order to properly evaluate the events pre-identified for compromised airway protection, a detailed baseline evaluation of the subject’s presence or

prior history of aspiration, aspiration pneumonia, choking, and dysphagia must be taken at screening and captured in the subject's source documents and eCRF.

To ensure that these events are consistently rated on the same criterion throughout the study, the definitions for diagnosis and intensity identified below should be used for baseline evaluations. This thorough baseline evaluation will assist the Investigator in determining, based on a clinical evaluation, whether or not occurrences of aspiration, aspiration pneumonia, choking, and dysphagia during the study qualify as adverse events, as defined in Section 16.2.1.

16.2.4.1 Aspiration and Aspiration Pneumonia

Definition

The presence of oral secretions, food substances, fluids, and/or gastric contents in the airways and/or the lungs may be the result of choking and/or dysphagia. Aspiration of small fragments of material can produce airway obstruction as well as lung abscesses. Aspiration of gastric contents with a low pH due to the presence of hydrochloric acid may injure the alveolar epithelium producing diffuse interstitial and alveolar edema. Anaerobic organisms may also be present in the lung and peripheral blood cultures.

ASPIRATION

Diagnosis

The diagnosis of aspiration should include:

- New onset of respiratory symptoms and one of the following without an alternative medical cause:
 - Abnormal chest examination (rales, wheezing)
 - Abnormal gas exchange
 - Abnormal chest x-ray

Supportive information –

- Recent diagnosis of aspiration pneumonia
- Recent diagnosis of dysphagia

Intensity

- Mild
 - Asymptomatic or associated with a cough
- Moderate (any one of the following)
 - Abnormal chest x-ray
 - Productive cough

- Abnormal lung examination (wheezing, rales)
- Hypoxia
- Severe (any one of the following)
 - Respiration compromise
 - Pneumonia
 - Pneumonitis

ASPIRATION PNEUMONIA

Diagnosis

One or more serial chest x-rays with one of the following:

- New or progressive and persistent infiltrate
- Consolidation
- Cavitation

And at least one of the following

- Fever ($>38^{\circ}\text{C}$) with no other cause
- Leukopenia ($<4,000$ white blood cells (WBC)/ mm^3) or leukocytosis ($>12,000$ WBC/ mm^3)

And at least one of the following

- New onset purulent* sputum or change in character of sputum
- New onset or worsening cough, or dyspnea, or tachypnea
- Rales or bronchial breath sounds
- Worsening gas exchange
- Cultures positive for anaerobes or mixed oral flora

* Purulent sputum includes secretions from the lungs, bronchi, or trachea that contain >25 neutrophils and <10 squamous epithelial cells per low power field (10X).

Supportive Information –

- Documentation of a temporal relationship between the onset of symptoms and the aspiration of fluids (e.g., gastric contents, inert liquids) or particulate matter (e.g., food)
- Positive peripheral blood and/or sputum culture

Intensity

- Mild (all of the following)

- Defervescence on oral antibiotics
- Satisfactory response to outpatient treatment
- No need for supplemental oxygen
- Moderate (any one of the following)
 - Hospitalized
 - Treated with intravenous antibiotics
- Severe (any one of the following)
 - Supplemental oxygen needed
 - Positive blood culture(s)
 - Invasive procedure required (intubation, lung biopsy, chest tube, surgery)
 - Presence of empyema, cavitation

16.2.4.2 Choking

Definition

Obstruction of the larynx, trachea, or esophagus by a partially swallowed foreign body, food, or liquid or laryngospasm may be described as choking.

Diagnosis

The diagnosis of choking should include:

- An observed episode with description of the circumstances and any inciting factor(s)
- Coughing with self clearance of obstruction or penetration of airway

Supportive Information –

- Recent diagnosis of aspiration pneumonia
- Recent diagnosis of dysphagia
- Imaging study such as a barium swallow

Intensity

- Mild
 - Occasional episode while eating or drinking (<once/day)
- Moderate
 - Frequent episodes while eating or drinking (≥once/day)
- Severe
 - Episode that requires intervention with or without loss of consciousness, may be associated with hypoxia

16.2.4.3 *Dysphagia*

Definition

Dysphagia is defined as difficulty swallowing (dys meaning difficulty/disordered and phagia meaning to eat). Depending on the severity and the neuromuscular component compromised, dysphagia can impair the subject's ability to swallow liquids (including saliva), solids or both. The normal swallow occurs in 3 phases: oral, pharyngeal, and esophageal with each phase lasting approximately one second. The oral phase is under voluntary neuromuscular control, whereas the pharyngeal and esophageal phases are involuntary requiring an intact swallowing reflex. Damage, compression, paralysis, and/or fatigue of the neuromuscular components may lead to dysphagia.

Diagnosis

The diagnosis of dysphagia should include:

- New onset of difficulty swallowing for solids, liquids or both
- Assessment of symptoms to identify other causes, such as dry mouth
- Clinical or radiographic observation and/or documentation of the subject's ability to swallow solids and liquids

Supportive Information –

- Recent episode of choking requiring intervention and/or treatment
- Repeated episodes of coughing while eating or drinking
- Recent diagnosis of aspiration pneumonia
- Imaging study such as a barium swallow

Intensity

- Mild
 - Occasional difficulty swallowing but no choking
- Moderate
 - Frequent difficulty swallowing with choking but able to eat and drink without assistance
- Severe
 - Inability to swallow liquids, solids or both without choking or medical intervention

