Subjects whose risk of aspiration are judged by the investigator to be satisfactorily controlled by placement of PEG or G-tube for nutritional support are eligible to participate. Specific criteria excluding subjects with moderate to severe dysphagia or choking within the last 6 months prior to screening have been removed, and instead the protocol focuses solely on the risk of aspiration, taking into consideration that those with a PEG or G-tube (in whom placement of either would mitigate the risk of aspiration associated with a moderate to severe risk dysphagia or choking) may participate. The previous exclusion criteria could be considered too vague or restrictive as it focused on a symptom (dysphagia or difficulty with swallowing) that is common to many neurological disorders and especially frequent in ALS. The

revised inclusion/exclusion criteria now focus on the baseline risk of aspiration because it is aspiration that can lead to significant morbidity and even mortality.

- The requirement to administer the Visual Analog Scale (VAS) to subjects in order to rate severity for dysphagia and dry mouth at every clinic visit has been removed. Administering the scale at every visit, regardless of a reported event of dysphagia or dry mouth, is unnecessary and would result in an overreporting of events. Adverse events of dysphagia and dry mouth will continue to be collected based on subject report and severity will be determined by the Investigator.

Study drug injections should not be administered if an adverse event of dysphagia or dry mouth of moderate to severe severity persists without prior consultation with the Medical Monitor. If the adverse event has not resolved or has not improved to a mild severity by the end of the per protocol window for injections to occur (every 13 ± 2 weeks), the Medical Monitor should be contacted to discuss whether or not the subject should be dosed, discontinued, etc.

- Administrative updates have been incorporated, including a change in the Medical Monitor information.

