11.1.2 Exclusion Criteria

Subjects who meet any of the following criteria will not be allowed to participate:

1. A moderate to high risk of aspiration will exclude participation in this study. Moderate to high risk of aspiration is defined by any one of the following:
 - History of aspiration pneumonia in the last 6 months before screening
 - Speech pathologist and/or formal swallowing test (e.g., with barium, endoscopy, dynamic swallowing study, imaging study, fiber-optic endoscopic swallowing evaluation or other imaging scan) that concludes that a moderate to severe risk of aspiration exists
 - Due to perceived risk of aspiration, a health care professional has recommended PEG or G-tube but subject declined
 - In the Investigator's clinical judgment, the subject is at moderate to high risk of aspiration.Subjects whose risk of aspiration are judged by the Investigator to be satisfactorily controlled by placement of PEG tube or G-tube for nutritional support are eligible to participate.
2. Respiratory FVC of <20% of predicted. FVC will be tested in all ALS subjects, and also in other subjects at Investigator discretion if warranted.
3. Prior botulinum toxin type A or B treatment in the salivary gland(s) identified for treatment in this study within 24 weeks before screening. Prior botulinum toxin type A or B treatment into other anatomical regions not selected for treatment in this study is not exclusionary, but must have occurred at least 12 weeks before screening.
 - In the Investigator's assessment, prior toxin exposure must have been well tolerated and without any significant long-term side effects in the case of repeated prior exposure. Subjects should be excluded if, in the Investigator's opinion, the subject failed to respond to previous treatment with botulinum toxin. Subjects should not receive nor have any plans for receiving any botulinum toxin treatment, other than the study drug (MYOBLOC), during the entire course of the study (from the point the informed consent is signed until subject's participation is complete).
4. Prior salivary gland surgery.
5. Concomitant use, or exposure within 5 half lives of screening, of aminoglycoside antibiotics, curare-like agents, or other agents that interfere with neuromuscular function.

6. Current treatment or treatment at any time during the study with Coumadin[®] (warfarin) or similar anti-coagulant medications. Anti-platelet medications are not specifically exclusionary.

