16.2.1 Definition of Adverse Event

An adverse event is defined as any untoward medical occurrence in a patient administered a medicinal product. An adverse event includes any noxious, pathologic, or unintended change in anatomic, physiologic, or metabolic functions as indicated by physical signs, symptoms and/or laboratory changes occurring in any phase of the clinical study whether associated with study drug, active comparator, or placebo, and whether or not considered to be drug related.

Examples include an exacerbation of pre-existing conditions or events, intercurrent illnesses, drug interaction, or the significant worsening of the disease under investigation that is not recorded elsewhere in the eCRF under specific effectiveness assessments. Anticipated fluctuations of pre-existing conditions that do not represent a clinically significant exacerbation or worsening need not be considered adverse events.

In clinical studies, an adverse event can include an undesirable medical condition occurring at any time during study participation, including run-in or wash-out periods, even if no study treatment has been administered.

Intercurrent illness and/or sequelae from intercurrent illness occurring between study screening/enrollment and dosing with study drug will be captured on the Adverse Event eCRF.

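### The dysphagia AESI definition has no worsening limb and its intensity scale has gaps, so worsening in subjects with existing dysphagia may be classed and graded inconsistently

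*Protocol*

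**What the plan says.** **Who can enter.** Exclusion 1 (Protocol Section 11.1.2) concerns aspiration risk, not dysphagia. It admits "Subjects whose risk of aspiration are judged by the Investigator to be satisfactorily controlled by placement of PEG tube or G-tube". The amendment summary (Section 1) confirms that this was deliberate: "Specific criteria excluding subjects with moderate to severe dysphagia or choking within the last 6 months prior to screening have been removed". It also describes the symptom as common in neurological disorders and especially so in ALS.

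**Diagnosis.** Under Section 16.2.4.3 the dysphagia diagnosis should include "New onset of difficulty swallowing for solids, liquids or both", an assessment for other causes, and observation or documentation of swallowing. None of the three elements refers to worsening. Section 16.1 applies these diagnosis and intensity definitions both to the baseline evaluation and to every later assessment.

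**What counts as an adverse event.** Section 16.2.1 gives as an example "an exacerbation of pre-existing conditions or events", and lets anticipated fluctuations without clinically significant worsening go unrecorded. Sections 16.1 and 16.2.4 send the Investigator to 16.2.1 to decide whether a later occurrence is an adverse event.

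**Intensity.** The dysphagia scale has three grades. The middle one, moderate, is defined as "Frequent difficulty swallowing with choking but able to eat and drink without assistance". The grade below it is for difficulty that is only occasional and comes without any choking. The grade above it is for subjects who cannot swallow unless they choke or receive medical help. Section 16.2.2.1 has a separate general scale for every adverse event, based on interference with daily activities.

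**Where the labels are used.** Section 16.2.8.1 requires AESIs to reach the Sponsor within 24 hours. Section 13.2 ties the Medical Monitor consultation before an injection to persistent dysphagia of moderate to severe grade. SAP Section 5.4 reports the incidence of subjects with an AESI per treatment session and gives no selection rule.

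**The concern.** Dysphagia is one of four AESIs, and AESI occurrence is a named safety endpoint in a study whose primary objective is safety. The protocol admits subjects who already have the condition, yet its AESI criterion describes only a first appearance. One site could class a clinically significant worsening as a dysphagia AESI, while another records it as an ordinary adverse event because the onset was not new. The AESI incidence would then depend partly on how each site reads one bullet.

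Grading has a similar weakness. An event that fits none of the dysphagia-specific grades must be placed by judgement, and the mild/moderate boundary has a use in Section 13.2. Amendment 01 also dropped the routine visual analogue rating of dysphagia at each visit and left severity to the Investigator, so the written scale carries more weight.

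**Working it through.** The plan gives no figure on this point, so there is none to reproduce. The check is a comparison of passages, a cross-tabulation of the scale, and an illustration on assumed inputs.

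**1. Is worsening dysphagia an adverse event?** Yes, if clinically significant: Section 16.2.1 says so, and 16.2.4 refers the decision there.

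**2. Is it a dysphagia AESI?** The documents do not say. Section 16.2.4.3 names new onset only. Section 16.2.1 settles adverse-event status but not AESI status. Elsewhere the protocol does write a worsening limb: aspiration pneumonia has "New onset or worsening cough, or dyspnea, or tachypnea".

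**3. What depends on the answer?** A serious worsening is reported within 24 hours in any case, because all serious adverse events are. A non-serious worsening is reported that fast only if it is classed as an AESI. Entry in the SAP Section 5.4 table depends on the same label, unless that table is built from preferred terms, which the SAP does not state.

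**4. Does the intensity scale cover every case?** For subjects below the severe grade who eat and drink unassisted:

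| Difficulty | No choking | With choking |
|---|---|---|
| Occasional | Mild | no grade |
| Frequent | no grade | Moderate |

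Two of the four cells have no dysphagia-specific grade. The general scale would give a grade in both, but it uses a different criterion. Frequent difficulty without choking that interferes with daily activities is moderate on the general scale. On the dysphagia scale it matches mild on choking and moderate on frequency. Section 16.1 points sites to the 16.2.4 scale and Section 16.2 points them to 16.2.2.1. Neither is given precedence.

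**5. How large could an under-count be?** Let N be the number of subjects, b the share with baseline dysphagia, r the new-onset rate in the others, and w the worsening rate in those with baseline dysphagia. Then:
- count including worsening = N × [(1 − b) × r + b × w]
- count under a strict new-onset reading = N × (1 − b) × r
- difference = N × b × w

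N = 187 is from SAP Section 2.5. The documents give none of b, r or w. With r = 5% assumed throughout:

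| b (assumed) | w (assumed) | Including worsening | Strict reading | Difference |
|---|---|---|---|---|
| 10% | 5% | 9.35 (5.0%) | 8.4 (4.5%) | 187 × 0.10 × 0.05 = 0.9 |
| 30% | 10% | 12.2 (6.5%) | 6.5 (3.5%) | 187 × 0.30 × 0.10 = 5.6 |
| 50% | 20% | 23.4 (12.5%) | 4.7 (2.5%) | 187 × 0.50 × 0.20 = 18.7 |

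Each difference assumes that every worsening is left out. If sites record worsening under 16.2.1 and class it as dysphagia AESI, the difference is 0 in every row.

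**The case against.** The strongest reply is that the protocol already handles worsening. The adverse-event decision rests on 16.2.1, which names exacerbation, and the detailed baseline evaluation exists so that later occurrences can be compared with it. The diagnosis only *should* include new onset. Because the same definitions are used at baseline, a strict new-onset test would make existing dysphagia undiagnosable at screening, which cannot be intended. The contrast with aspiration pneumonia is also weak: worsening there qualifies one symptom among several alternatives, and the criterion for plain aspiration, like that for dysphagia, mentions new onset only. SAP Section 5.4 applies no new-onset filter. Dysphagia recorded as an adverse event also reaches the general tables by preferred term and the distant-spread table (SAP Section 5.6). Finally, every adverse event is graded under 16.2.2.1, and choking is an AESI with its own frequency grades.

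Most of this stands. Worsening can be recorded, no event need go without some grade, and the SAP excludes nothing explicitly. Two things remain. No passage says that worsening is a dysphagia *AESI*, the label that governs 24-hour reporting and the AESI table. No passage says which intensity scale prevails when the dysphagia scale has no matching cell or the two scales disagree.

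A reader might go further and infer that subjects with baseline dysphagia cannot meet the AESI diagnosis, or that AESI incidence is biased low in proportion to their share. The documents support neither. The first reads one bullet apart from 16.2.1. The second assumes that every worsening is lost, and the documents give neither the share of such subjects nor an event rate.

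**Conclusion.** The point holds as an inconsistency to be reconciled. It does not show that events are lost. Section 16.2.4.3 and Section 16.2.1 differ on worsening, and the dysphagia scale leaves two of four sub-severe combinations without a grade while competing with a general scale of unstated rank. Sites that follow the text literally can class and grade the same event differently on a named safety endpoint.

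The size is unknown. It is zero if sites apply 16.2.1 and class worsening as dysphagia AESI. On a fully strict reading it is about 1 to 19 of 187 subjects across the three assumed scenarios above. Those figures show scale only and are not estimates. How often events fall in the two ungraded cells cannot be judged from the documents either.

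**What to change.** 1. **Protocol Section 16.2.4.3, diagnosis.** Word the criterion as *new onset, or worsening relative to the screening baseline evaluation*, so that it agrees with 16.2.1 and uses the evaluation that 16.2.4 already requires.
2. **Protocol Sections 16.2.4.3 and 16.2.2.1, intensity.** Reconcile the two scales so that each combination of frequency and choking maps to exactly one grade, and state which scale governs. The sponsor's clinicians decide the grades, knowing that Section 13.2 uses the mild/moderate boundary.
3. **SAP Section 5.4.** State that dysphagia AESIs include recorded worsening events, and give the selection rule. One option is every treatment-emergent event with the dysphagia preferred term, whatever label the site attached. Show the incidence by baseline dysphagia status, which is collected at screening (Protocol Section 16.2.4, SAP Section 2.6.3).

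The cost is a short amendment with site guidance, a few lines in the SAP and one added breakdown. The AESI count may rise slightly. The SAP is dated July 2018, and its Section 3.4 already reports how many subjects separate the two populations, so data collection may be finished. In that case only item 3 can be applied: it makes the table's rule explicit but cannot recover events that were never recorded or make past grading uniform.

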16.2.5 Pregnancy

Although pregnancy is not considered an adverse event, it is the responsibility of the Investigator to report any pregnancy in a subject (spontaneously reported to them or discovered during a protocol-defined pregnancy test) that occurs during the study or within

13 weeks after the last injection of study drug. All subjects who become pregnant must be withdrawn from the study and must be followed to the completion/termination of the pregnancy. If the pregnancy continues to term, the outcome (health of infant) and status of mother and child must also be reported to the Sponsor.

16.2.6 Serious Adverse Events

An SAE or serious adverse drug experience is any untoward medical occurrence at any dose that:

- Results in death during the period of protocol-defined surveillance;
- Is life-threatening (*NOTE: The term "life-threatening" in the definition of "serious" refers to an event in which the subject, in the view of the Investigator, was at immediate risk of death at the time of the event; it does not refer to an event which hypothetically might have caused death if it were more severe*);
- Requires inpatient hospitalization or prolongation of existing hospitalization* ;
- Results in persistent or significant disability or incapacity; and
- Results in a congenital anomaly/birth defect.

* Hospitalization: Out-patient treatment in an emergency room is not in itself an SAE, although the reasons for it might be (e.g., bronchospasms, laryngeal edema). Hospital admission and/or surgical operations planned before or during a study are not considered SAEs if the illness or disease existed before the subject was enrolled in the study, provided that it did not deteriorate in an unexpected way during the study. It should be noted that for this study, subjects with planned or anticipated surgery should not be enrolled into the study.

Important Medical Events: Medical and scientific judgment should be exercised in deciding whether a case is serious in situations where important medical events may not be immediately life-threatening or result in death, hospitalization, disability, or incapacity but may jeopardize the subject or may require medical or surgical intervention to prevent one or more outcomes listed in the definition of serious. These should usually be considered as serious, and examples of such events are:

- Angioedema not severe enough to require intubation but requiring intravenous hydrocortisone treatment;
- Hepatotoxicity caused by paracetamol (acetaminophen) overdose requiring treatment with N-acetylcysteine;
- Intensive treatment in an emergency room or at home for allergic bronchospasms; and
- Development of drug dependency or drug abuse.

All SAEs will be assessed by the Investigator as detailed in Section 16.2.2.

